Annex Table 2. RBC Transfusion Codes

Code	Description	Code Type
3643 0	Transfusion, blood or blood components	CPT

Mark Committee of the C	December 2024	
3644 0	Push transfusion, blood, 2 years or under	CPT
3645 0	Exchange transfusion, blood, newborn	CPT
3645 5	Exchange transfusion, blood; other than newborn	CPT
3645 5	EXCHNG TRANSFUSION BLOOD OTHER/THAN NEW BORN	CPT
3651 6	Therapeutic apheresis; with extracorporeal immunoadsorption, selective adsorption, or selective filtration and plasma reinfusion	CPT
P901 0	BLOOD (WHOLE), FOR TRANSFUSION, PER UNIT	HCPC S
P901 1	BLOOD, SPLIT UNIT	HCPC S
P901 6	Red blood cells, leukocytes reduced, each unit	HCPC S
P902 1	Red blood cells, each unit	HCPC S
P902 2	Red blood cells, washed, each unit	HCPC S
P903 8	Red blood cells, irradiated, each unit	HCPC S
P903 9	Red blood cells, deglycerolized, each unit	HCPC S
P904 0	Red blood cells, leukocytes reduced, irradiated, each unit	HCPC S
P905 1	Whole blood or red blood cells, leukocytes reduced, cmv-negative, each unit	HCPC S
P905 4	Whole blood or red blood cells, leukocytes reduced, frozen, deglycerol, washed, each unit	HCPC S
P905 7	Red blood cells, frozen/deglycerolized/washed, leukocytes reduced, irradiated, each unit	HCPC S
P905 8	Red blood cells, leukocytes reduced, cmv-negative, irradiated, each unit	HCPC S
3023 0N1	Transfusion of Nonautologous Red Blood Cells into Peripheral Vein, Open Approach	ICD10 PROC

V 2.0 23 1	December 2024	
3023	Transfusion of Nonautologous Frozen Red Cells into Peripheral Vein, Open	ICD10
0P1	Approach	PROC
3023	Transfusion of Nonautologous Red Blood Cells into Peripheral Vein,	ICD10
3N1	Percutaneous Approach	PROC
3023	Transfusion of Nonautologous Frozen Red Cells into Peripheral Vein,	ICD10
3P1	Percutaneous Approach	PROC
3024	Transfusion of Nonautologous Red Blood Cells into Central Vein, Open	ICD10
0N1	Approach	PROC
3024	Transfusion of Nonautologous Frozen Red Cells into Central Vein, Open	ICD10
0P1	Approach	PROC
3024 3N1	Transfusion of Nonautologous Red Blood Cells into Central Vein, Percutaneous Approach	ICD10 PROC
3024	Transfusion of Nonautologous Frozen Red Cells into Central Vein,	ICD10
3P1	Percutaneous Approach	PROC
3025	Transfusion of Nonautologous Red Blood Cells into Peripheral Artery, Open	ICD10
0N1	Approach	PROC
3025	Transfusion of Nonautologous Frozen Red Cells into Peripheral Artery, Open	ICD10
0P1	Approach	PROC
3025	Transfusion of Nonautologous Red Blood Cells into Peripheral Artery,	ICD10
3N1	Percutaneous Approach	PROC
3025	Transfusion of Nonautologous Frozen Red Cells into Peripheral Artery,	ICD10
3P1	Percutaneous Approach	PROC
3026	Transfusion of Nonautologous Red Blood Cells into Central Artery, Open	ICD10
0N1	Approach	PROC
3026	Transfusion of Nonautologous Frozen Red Cells into Central Artery, Open	ICD10
0P1	Approach	PROC
3026	Transfusion of Nonautologous Red Blood Cells into Central Artery,	ICD10
3N1	Percutaneous Approach	PROC
3026	Transfusion of Nonautologous Frozen Red Cells into Central Artery,	ICD10
3P1	Percutaneous Approach	PROC
6A55 0Z0	Pheresis of Erythrocytes, Single	ICD10 PROC
6A55 1Z0	Pheresis of Erythrocytes, Multiple	ICD10 PROC

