An important non-pharmacologic intervention for SCD is RBC transfusion.³ RBC transfusions are indicated for severe symptomatic anemia, acute complications like stroke or acute multi-organ failure, and/or secondary prevention of stroke or recurrent pain crises in individuals with SCD.³ The two primary types of RBC transfusions, simple (addition of RBCs without removal of the patient's blood) and exchange (removal of the patient's blood and replacement with donor packed RBCs), have both acute and chronic indications. Treatment guidelines recommend acute transfusions for symptomatic anemia, ACS, multiorgan failure, and preoperatively; chronic transfusions, usually administered monthly,

are recommended for stroke prevention.³ While blood transfusions can improve SCD complications, they are also associated with important risks that can occur at each transfusion: resultant iron overload can lead to end organ damage, alloimmunization can lead to delayed hemolytic transfusion reactions (DHTR) and mortality, and transfusion transmitted infections can cause organ damage and mortality.^{3,8–11} Additionally, transfusion administration can be burdensome to patients due to the need for frequent venous access, which can cause pain, psychological distress, and interruptions to daily life.¹² A significant unmet need exists for new therapies and interventions that address the clinical complications of SCD while mitigating the patient burden.

Once-daily oral administration of voxelotor has been shown to reduce red-cell sickling, blood viscosity and improve red-cell deformability in vitro and to extend red-cell half-life and reduce anemia and hemolysis in vivo. ¹³ Evidence from clinical studies has demonstrated that voxelotor has a beneficial effect on Hb levels, a critical factor in the decision for an RBC transfusion. However, no clinical trials have demonstrated the impact of voxelotor on rates of RBC transfusion. While preliminary real-world evidence (RWE) supports a reduction in RBC transfusions associated with voxelotor use, these studies are limited by small sample sizes and lack of comparator populations. ^{14,15}

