	Definition 2 (sensitivity analysis, broad definition): • Presence of ICD-10 diagnoses code for VOCs (definition 1) and/or VOC component (e.g., ACS, priapism, stroke, splenic sequestration, or crisis unspecified) on a claim from one of the following healthcare settings:	

V2.0 23 December 2024	T s	
	 Telemedicine visit Office clinic visit: Outpatient visit Urgent care visit Emergency visit Inpatient visit 	
	Final definition to be included in SAP.	
Venous Thromboembolism	Presence of an ICD-10-CM diagnosis code on any claim	
Avascular Necrosis	Presence of an ICD-10-CM diagnosis code on any claim	
Cholelithiasis	Presence of an ICD-10-CM diagnosis code on any claim	
Chronic Kidney Disease	Presence of an ICD-10-CM diagnosis code on any claim	
Chronic Pain	Presence of an ICD-10-CM diagnosis code on any claim	
Diabetes	Presence of an ICD-10-CM diagnosis code on any claim	
Heart Failure	Presence of an ICD-10-CM diagnosis code on any claim	
Iron Overload	Presence of an ICD-10-CM diagnosis code on any claim	
Leg Ulcer	Presence of an ICD-10-CM diagnosis code on any claim	
Pulmonary Hypertension	Presence of an ICD-10-CM diagnosis code on any claim	
Retinopathy	Presence of an ICD-10-CM diagnosis code on any claim	
Treatments		
Voxelotor	Presence of a national drug code (NDC) or generic name on a pharmacy event claim	

7	12	0	23	D	ecem	her	20	24

1 - 1 - 1 - 1 - 1 - 1 - 1 - 1 - 1 - 1 -	
Hydroxyurea	Presence of a national drug code (NDC) or generic name on a pharmacy event claim
Crizanlizumab	Presence of a national drug code (NDC) or generic name on a pharmacy event claim
	OR
	Presence of an ICD-10-CM procedure, Current Procedural Terminology (CPT), or Healthcare Common Procedure Coding System (HCPCS) code on any claim
L-glutamine	Presence of a national drug code (NDC) or generic name on a pharmacy event claim
Erythropoietin Stimulating Agent	Presence of a national drug code (NDC) or generic name on a pharmacy event claim
(ESA)	OR
	Presence of an ICD-10-CM procedure, Current Procedural Terminology (CPT), or Healthcare Common Procedure Coding System (HCPCS) code on any claim
Other Covariates	
RBC transfusion	Presence of an ICD-10-CM procedure, Current Procedural Terminology (CPT), or Healthcare Common Procedure Coding System (HCPCS) code on any claim
	Multiple codes or claims occurring on the same day will be assessed as a single RBC transfusion event.
Hb lab test	Presence of a LOINC or CPT/HCPCS code,
	OR no presence of a LOINC or CPT/HCPCS code

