Hb value	Presence of a LOINC code,
	AND
	A non-missing, numeric lab result value
Healthcare Interactions - Inpatient/Outpatient Visit	Presence of any claim in the following tables:

7	12	0	23	D	ecem	her	2.0	124	Ī

resence of an ICD-10-CM diagnosis code on any claim
resence of a national drug code (NDC) or generic name on a pharmacy vent claim
DR .
Presence of an ICD-10-CM procedure, Current Procedural Terminology CPT), or Healthcare Common Procedure Coding System (HCPCS) code in any claim
resence of an ICD-10-CM diagnosis code on any claim
resence of an ICD-10-CM diagnosis code on any claim
CCI (continuous)
ee SCD comorbidities definition above
resence of an ICD-10-CM diagnosis code on any claim
resence of an ICD-10-CM diagnosis code on any claim
resence of an ICD-10-CM diagnosis code on any claim
resence of an ICD-10-CM diagnosis code on any claim
resence of an ICD-10-CM diagnosis code on any claim
resence of an ICD-10-CM diagnosis code on any claim
resence of an ICD-10-CM diagnosis code on any claim

VZ.0 Z5 December Z0Z1	
Mild Liver Disease	Presence of an ICD-10-CM diagnosis code on any claim
Diabetes Without Chronic Complication	Presence of an ICD-10-CM diagnosis code on any claim
Diabetes With Chronic Complication	Presence of an ICD-10-CM diagnosis code on any claim
Hemiplegia or Paraplegia	Presence of an ICD-10-CM diagnosis code on any claim
Renal Disease (Mild to Moderate)	Presence of an ICD-10-CM diagnosis code on any claim
Renal Disease (Severe)	Presence of an ICD-10-CM diagnosis code on any claim
Any Malignancy Without Metastasis Including Leukemia and Lymphoma	Presence of an ICD-10-CM diagnosis code on any claim
Moderate or Severe Liver Disease	Presence of an ICD-10-CM diagnosis code on any claim
Metastatic Solid Tumor	Presence of an ICD-10-CM diagnosis code on any claim
Human immunodeficiency virus	Presence of an ICD-10-CM diagnosis code on any claim
Acquired Immunodeficiency Syndrome	Presence of an ICD-10-CM diagnosis code on any claim
Patient-Level Outcome I	Definitions
RBC transfusions	For each patient, the number of RBC transfusions will be evaluated PPPY in baseline and follow-up. See covariate definition above for operational definition and Table 5 for output definition. See Annex Table 2 for RBC transfusion codes.
Stroke (including transient ischemic attack)	For each patient, stroke will be evaluated as the time to stroke in days. See covariate definition above for operational definition and Table 5 for output definition.

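### The primary-outcome code list includes CPT 36516, a plasma-reinfusion apheresis procedure that by its printed descriptor is not a red-cell transfusion

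*Protocol*

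**What the plan says.** The outcome entry for RBC transfusions in Annex Table 1 sends the reader to the code list: "See Annex Table 2 for RBC transfusion codes". The same table defines an event as "Presence of an ICD-10-CM procedure, Current Procedural Terminology (CPT), or Healthcare Common Procedure Coding System (HCPCS) code on any claim", with one limit: "Multiple codes or claims occurring on the same day will be assessed as a single RBC transfusion event". No second, confirming code is required.

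Annex Table 2 holds four kinds of entry:

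- **CPT:** 36430, 36440, 36450, 36455 (printed twice) and 36516. The descriptor of 36516 is "Therapeutic apheresis; with extracorporeal immunoadsorption, selective adsorption, or selective filtration and plasma reinfusion". That of 36430 is "Transfusion, blood or blood components".
- **HCPCS:** twelve product codes for whole blood or red cells.
- **ICD-10 procedure codes for transfusion:** red cells or frozen red cells, by vessel and approach.
- **ICD-10 procedure codes for apheresis:** 6A550Z0, "Pheresis of Erythrocytes, Single", and 6A551Z0, its counterpart for multiple procedures.

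Section 7 describes two types of transfusion. Simple transfusion adds red cells without removing blood. The other is "exchange (removal of the patient's blood and replacement with donor packed RBCs").

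Table 2 in Section 9.2.1 defines the entry criterion of at least two baseline transfusions by ICD-10-PCS procedure codes only. It mentions neither CPT nor HCPCS codes.

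**The concern.** A code list for red-cell transfusion should admit only procedures in which red cells are given, or should explain why it is broader. CPT 36516 does not meet that test on its printed descriptor, and the event rule lets it count unaided. The same list supplies the baseline count, the follow-up count and, through the baseline count, a candidate propensity-score covariate (Table 4). A wrong row therefore reaches the sole primary endpoint of a study whose reports are to go to FDA and EMA (Section 12).

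Three related points need attention:

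- CPT 36430 covers blood components in general, so by its wording a day with only a non-red-cell component also counts.
- The list recognises erythrocyte pheresis only in ICD-10-PCS. Its one apheresis row in CPT is the plasma-reinfusion procedure.
- Entry and outcome are defined on different code systems.

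Table 7 plans no alternative transfusion definition that would show how much any of this matters. VOC, by contrast, is given a strict and a broad definition.

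**Working it through.** **Does 36516 fit the protocol's own concept of transfusion?**

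| Source | What is given to the patient |
|---|---|
| Section 7, simple transfusion | red cells, no removal |
| Section 7, exchange transfusion | donor packed red cells, after removal |
| Annex Table 2, CPT 36516 | reinfused plasma, after adsorption or filtration |

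The third row matches neither of the first two.

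**Does it count alone?** Yes. Annex Table 1 needs only the presence of one listed code on a claim. Same-day collapsing limits the damage: if any other listed code falls on that day, the day is already one event and 36516 adds nothing. False events arise only on days where 36516 is the sole listed code.

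**What does a false event do to one patient?** Section 9.7.3 annualises the follow-up count as events / days × 365.

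- At 365 days: 1/365 × 365 = 1 per year.
- At 180 days (the enrolment required after index): 1/180 × 365 = 2.03 per year.
- In baseline, one false event adds 1 per year, which makes the change from baseline 1 lower.

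**What does it do to the group contrast?** Section 9.5 sizes the study at 185 treated and 370 controls for a mean difference of 1.

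- One false follow-up event in one treated patient: 1/185 = 0.005 at 365 days; 2.03/185 = 0.011 at 180 days.
- One in one control: 1/370 = 0.003; 2.03/370 = 0.005.
- To shift the treated mean by the whole design difference at full follow-up: 1 × 185 = 185 net false events in that arm.

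**Noise or bias?** Let F be the mean annual rate of false events, by arm (T, C) and period (base, fu). The primary analysis is a difference in mean change with an identity link, so

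bias = (F_T,fu − F_T,base) − (F_C,fu − F_C,base).

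This is zero if the false-event rate is stable over time in each arm, or if it changes equally in both. False events then add variance only. Bias appears when the change after index differs between arms. The documents give no value of F for any cell, so the bias cannot be computed.

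**Is red-cell exchange missed?** The list holds CPT 36455 ("Exchange transfusion, blood; other than newborn"), twelve HCPCS product codes and two erythrocyte-pheresis ICD-10-PCS codes. Any one of them is enough. An exchange is lost only on a day carrying none of them, and the documents do not show that such days occur.

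**Does the validation work settle it?** Annex Table 3 reports 181/200 = 90.5% of reviewed episodes with a documented transfusion within 3 days, leaving 19/200 = 9.5% without. No cause is given for the 19. The concordance objective in Section 9.4 refers to ICD-10 procedure codes. The result therefore neither validates 36516 and 36430 nor implicates them.

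**The case against.** The strongest defence is that this may be one row of negligible frequency. Same-day collapsing already limits it, and a single event barely moves a mean over 185 patients. Code lists are also to accompany the SAP, which is not shown, and Section 9.3 has all codes reviewed by the protocol authors and a Scientific Review Committee. The points on frequency and size stand. The appeal to later documents does not cure the row: it is printed in the list that Annex Table 1 makes the outcome definition, and Section 9.7 says major changes to primary endpoint definitions would be reflected in a protocol amendment.

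For 36430, the sponsor can fairly say that a broad code trades specificity for sensitivity, and no frequency of platelet-only or plasma-only days is given. That supports a sensitivity analysis, not removal.

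A reader might infer more than the documents support:

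- **That red-cell exchange is under-counted because the intended CPT code was left out.** Nothing in the protocol shows that such a code exists or that exchanges are billed under it alone, and several listed codes would capture an exchange.
- **That one false event equals the difference the study is sized for.** That difference is a group mean, not one patient's count.
- **That random false events dilute the effect.** Under an identity-link comparison of mean changes, equal false events add variance and leave the expected difference unchanged.
- **That 36516 determines eligibility.** Read literally, Table 2 admits only ICD-10-PCS codes, so 36516 would not count towards entry.

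**Conclusion.** The point holds as a specific coding error. As written, the plan counts a procedure without red-cell transfusion as a primary-outcome event whenever it is the only listed code on a day. This follows from the printed descriptors and the event rule and needs no outside source.

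Its size is unknown. The likely form is added noise; bias requires that such procedures change differently by arm after index, and the documents give no evidence either way. It is not established that the primary outcome is materially misclassified. The correction is still warranted because the error sits in the definition of the only primary endpoint and is nearly free to remove.

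The mismatch between Table 2 and the Annex tables is a separate internal inconsistency. As it stands, the transfusions that qualify a patient and those counted as that patient's baseline rate need not be the same set. The per-event figures assume the planned 185 and 370 patients with equal weights.

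**What to change.** 1. Delete CPT 36516 from Annex Table 2 and re-run the baseline and follow-up counts before outcomes are examined by arm.
2. Report how many events rested on 36516 alone.
3. Verify, and state, how red-cell exchange billed on CPT claims is captured, since the list recognises erythrocyte pheresis only in ICD-10-PCS.
4. Add a sensitivity analysis of the primary endpoint that counts 36430 only when an RBC product code or an RBC ICD-10-PCS code is on the same day.
5. Reconcile the entry criterion in Table 2 (ICD-10-PCS only) with Annex Tables 1 and 2 (CPT and HCPCS as well), so that entry and baseline count rest on one stated definition.

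The cost is a code-list edit, a re-run and one extra analysis; no new data are needed. The downside is that the list may then differ slightly from the one used in the sponsor's validation study. The report should state this.

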Annex Table 3. Addressing Potential Real-World Data Limitations and Concerns

Variable	Potential concern	Supportive Data and/or Rationale	Study Design Mitigation
RBC transfusion outcome	Misclassification bias	Gu et al. found that 42,106 out of 46,381 (91%) RBC transfusion medical records in patients with SCD from Optum documented having a medical claim. Random sample of 200 RBC transfusion episodes were reviewed with associated free text notes. Of the 200 RBC transfusions, 181 (90.5%) had documentation of an RBC transfusion within 3 days of the procedure claim. ¹	Medical claims data will be used to measure the RBC transfusion outcome in this study. Prior studies support that medical claims are an accurate source for RBC transfusion, and no evidence exists of misclassification bias. If missingness occurred, no theoretical basis for differential misclassification between exposed/unexposed groups exists.
Hydroxyurea exposure	Known confounder	Hydroxyurea increases hemoglobin F and has demonstrated in clinical studies to decrease the proportion of individuals with SCD to receive at least 1 RBC transfusion.	captured from pharmacy prescription claims. Patients are required to have continuous enrollment in their pharmacy and medical benefits, so limited missing data should exist for hydroxyurea claims. Hydroxyurea will be included in the propensity score model as a covariate and both groups will have similar prior exposure to hydroxyurea. Similarly, as a sensitivity analysis will be performed to report the results stratified by prior treatment exposure to hydroxyurea,
Covariates	Misclassification bias	There is a possibility of missing information for patients is expected to be low but possible if patients seek healthcare without the use of medical or pharmacy insurance.	crizanlizumab, L-glutamine, and/or ESA. Since all patients regardless of exposure status will be required to have continuous enrollment over the period that covariates will be assessed if missingness occurred, no theoretical basis for differential misclassification between exposed/unexposed groups exists.
Hb labs	Missingness	Based on preliminary data explorations, approximately 17% of patients have at least one Hb result during the study timeframe. All lab values have an associated date and time.	Due to missingness in Hb lab results, Hb cannot be adjusted for in the primary analysis; however, a sensitivity analysis is planned that will stratify by baseline Hb and a separate propensity score model will be used to adjust for Hb results.

SCD genotype	Missingness	It is more likely severe genotypes (e.g., HbSS) should be requiring more than 2 RBC transfusions in the past year.	RBC transfusion by SCD genotype will be assessed in sensitivity analysis.
		Based on preliminary data explorations, approximately 93% have patients have genotype documented in our data set.	
Comorbidities	Missingness	There is a possibility of missing information for patients is expected to be low but possible if patients seek healthcare without the use of medical or pharmacy insurance.	Continuous enrollment in a health plan is required as part of the analysis. Thus, all healthcare interactions through insurance will be captured and including documented comorbidities recorded in medical billing records. If missingness occurred, no theoretical basis for differential documentation between exposed/unexposed groups exists. Propensity score adjustment aggregates the probability of exposure to voxelotor. It is expected that more severe diseases that would have a larger impact on outcomes would be better captured in the data ² and that limited underreporting of non-severe comorbidities should not have a substantial impact on the overall results.
Treatment adherence	Missingness	These data are not missing. Komodo data has near 100% of patients' pharmacy claims when requiring patients to have continuous enrollment in the pharmacy benefit. For exposed patients, we have 100% of the voxelotor claims through the use of Claritas data.	including as-treated and intent- to-treat analysis to ensure consistent results that best represent a RCT.
Race/ethnicity	Unmeasured confounder	Based on preliminary data explorations, approximately 90% of SCD patients have documented race/ethnicity in our data set. CDC estimates more than 90% are non-Hispanic Black or African American, and an estimated 3%–9% are Hispanic or Latino.	and is not missing from our data set.
Genetic factors	Unmeasured confounder	SCD genotype is captured in our data set. We are not aware of any other genetic factors that are important in the exposure- outcome relationship of interest.	Supplied the desired of the supplied of the su
SCD Severity	Unmeasured confounder	SCD severity is not currently defined in the literature. We will have patients SCD genotype, comorbidities, Charleson	SCD genotype, comorbidities, Charleson Comorbidity Index, and past healthcare utilization

Document Approval Record

Document Name: Document Title:		
Simular Duri	Dete/CMT)	Simple Consists
Signed By:	Date(GMT)	Signing Capacity
